13.4.1.7 Modification 7: the definition of serious adverse event (SAE) was revised

Rationale for change: Clarification of SAE definition and to align with Bayer internal language for SAE definition.

Sections affected by this modification:

- [Section 7.4.1.1.2 Serious adverse event \(SAE\)](#)

13.4.1.8 Modification 8: definition of USADE was clarified

Rationale for change: Since the protocol defines UADE and USADE separately but in the CFR the term UADE in fact refers to serious adverse events, a statement was added in the protocol to avoid confusion.

Sections affected by this modification:

- [Section 7.4.1.1.2.2 Unanticipated serious adverse device effect \(USADE\)](#)

13.4.1.9 Modification 9: perforations and potential allergy/hypersensitivity to Essure inserts were added to the Important Medical Events and events of special interest

Rationale for change: To collect information on perforations of the uterus, cervix or fallopian tubes and to help identify any study subjects who develop potential allergy or hypersensitivity to Essure inserts.

Sections affected by this modification:

- [Section 7.4.1.1.5 Important Medical Events and events of special interest](#)

13.4.1.10 Modification 10: instructions for the Investigator to assess whether an AE is an unanticipated adverse device effect were removed

Rationale for change: Change was made in order to align with Bayer safety reporting processes. Following the change in sponsor of this study from Conceptus to Bayer, this

question is no longer required to be answered by the investigator as this is an internal sponsor assessment.

Sections affected by this modification:

- [Section 7.4.1.3 Assessments and documentation of adverse events](#)

13.4.1.11 Modification 11: addition of a new section regarding device removal

Rationale for change: Addition of a device removal CRF to obtain more robust information regarding device removals.

Sections affected by this modification:

- [Section 7.4.2 Device removal](#)

13.4.1.12 Modification 12: minor edits and clarifications

Rationale for change: Minor edits and clarifications that were not previously identified in protocol Amendment 5.

Sections affected by this modification:

- [Title page](#)
- [Section 7.4.1.4 Reporting of serious adverse events](#)
- [Section 14 Appendices](#)

13.4.2 Changes to the protocol text

In this section, all affected protocol sections are detailed; the sequence of the sections follows the structure of the original protocol. In the display of modifications, the “old text” refers to the protocol version preceding this amendment. Deletions are crossed out in the “old text”. Additions are underlined in the “new text”. Corrections of typing errors or omissions are not highlighted in this amendment. Specific changes to the text are described by section below.

13.4.2.2 Synopsis

Section revised per modification 1.

Old text:

| | |
|--|--|
| Diagnosis and main criteria for inclusion | 
[...]
 
 Subject has a successful Essure Confirmation Test with satisfactory micro-insert location and fallopian tube occlusion in both tubal ostia documented in her subject record. 
[...]
 |
|--|--|

New text:

| | |
|--|--|
| Diagnosis and main criteria for inclusion | 
[...]
 
 Subject has a successful Essure Confirmation Test showing bilateral satisfactory micro-insert location (when using transvaginal ultrasound [TVU]) or both bilateral satisfactory location and tubal occlusion (when using a modified hysterosalpingogram [HSG]) documented in her subject record. 
[...]
 |
|--|--|

13.4.2.3 Section 2 Study objectives

Section revised per modification 2.

Old text:

The objectives of this study are to:

- Evaluate the contraceptive failure rate of Essure when NovaSure is performed following a successful Essure Confirmation Test, and

[...]

New text:

The objectives of this study are to:

- Evaluate the contraceptive failure rate of Essure when NovaSure is performed following a successful Essure Confirmation Test*, and

[...]

* Successful Essure Confirmation Test = satisfactory bilateral micro-insert location and fallopian tube occlusion when using HSG, or satisfactory or optimal bilateral micro-insert location and retention in both tubal ostia when using transvaginal ultrasound (TVU) (i.e. the subject is able to rely on Essure for contraception). Note: all subsequent descriptions of "successful" Essure confirmation test refer to this definition.

13.4.2.4 Section 5.1.1 Inclusion criteria

Section revised per modification 1.

Old text:

[...]

3. Subject has a successful Essure Confirmation Test ~~with~~ satisfactory micro-insert location ~~and fallopian tube occlusion in both tubal ostia~~ documented in her subject record

[...]

New text:

[...]

3. Subject has a successful Essure Confirmation Test showing bilateral satisfactory micro-insert location (when using transvaginal ultrasound [TVU]) or both bilateral satisfactory insert location and tubal occlusion (when using a modified hysterosalpingogram [HSG]) documented in her subject record

[...]

13.4.2.5 Section 5.2.1 Withdrawal

Section revised per modification 3.

Old text:

[...]

- If, in the investigator's opinion, continuation of the study would be harmful to the subject's well-being

~~Subjects may be withdrawn from the study for the following reasons:~~

- ~~• At the specific request of the sponsor and in liaison with the investigator (e.g. obvious non-compliance, safety concerns).~~

Subjects may be terminated from the study by the Investigator. Reasons for termination of a subject from the study may include, but are not limited to, the following:

[...]

New text:

[...]

- If, in the investigator's opinion, continuation of the study would be harmful to the subject's well-being

Subjects may be terminated from the study by the Investigator. Reasons for termination of a subject from the study may include, but are not limited to, the following:

[...]

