5.2 Withdrawal of subjects from study²¹

5.2.1 Withdrawal²² - amended

Subjects *must* be withdrawn from the study for the following reasons:

- At their own request or at the request of their legally acceptable representative
- At any time during the study and without giving reasons, a subject may decline to participate further. The subject will not suffer any disadvantage as a result.
- If, in the investigator's opinion, continuation of the study would be harmful to the subject's well-being

Subjects may be terminated from the study by the Investigator. Reasons for termination of a subject from the study may include, but are not limited to, the following:

- Subject does not retain device (e.g. due to removal of device, expulsion, salpingectomy or other utero-tubal surgeries)

¹⁹ Per Amendment 4 and 5

²⁰ Per Amendment 4

²¹ New section from sponsor template per Amendment 4

²² Withdrawal criteria adapted to suit a device meant for permanent wearing per Amendment 6.

- Death
- An adverse event (AE) preventing study participation
- Lost to follow-up and inability to contact the subject. Note that if a subject who is lost to follow-up is re-contacted, the subject will not be considered to have withdrawn from the study.

A subject who discontinues study participation prematurely for any reason is defined as a “dropout” if the subject has already undergone the NovaSure procedure.

A subject who, for any reason (e.g. failure to satisfy the selection criteria), terminates the study before the time point used for the definition of “dropout” (see above) is regarded a “screening failure”.

Any subject removed from the trial will remain under medical supervision until discharge or transfer is medically acceptable.

In all cases, the reason for withdrawal must be recorded in the case report form (CRF) and in the subject's medical records.

Details for the premature termination of the study as a whole (or components thereof [e.g. centers, treatment arms, dose steps]) are provided in Section 10 (Premature termination of the study).

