7.1.2.4 One-, Two- and Three-Year Post-EA Phone Call (\pm 28 days) - *amended*

One, two-, and three- years (\pm 28 days) from the date of the NovaSure EA procedure, the subject will be contacted by the physician's office to have a telephone follow-up visit. During each of these visits, designated study staff will conduct subject interview to:

- Confirm subject is not currently pregnant or has not been pregnant in the previous year
- Inquire whether or not any adverse events occurred over the past year
- Conduct subject interview to obtain information on subject satisfaction and comfort with wearing the micro-inserts post-NovaSure EA procedure
- Discuss whether or not subject has had or will have any extirpative surgery
- Confirm subject contact information
- Discuss any additional issues subject or the Investigator may have

The 3-year phone call will be the final visit in the study. If the subject reports a serious adverse event or pregnancy during the 3-year follow-up phone call, the subject will be followed by the sponsor's pharmacovigilance department until event resolution or stabilization. If a pregnancy or serious adverse event was previously reported but the event is not resolved during the 3-year phone call, the event will be followed by the sponsor's

²⁷ Per Amendment 4

pharmacovigilance department until resolution. Information pertaining to these events will be collected and archived in the sponsor's pharmacovigilance database.²⁸

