7.1.2.5 Notification of Other Relevant Events

The subject should be instructed at the beginning of the study to inform the site immediately if subject has had or is scheduled to have any surgery which may remove some or all of her reproductive organs (i.e. hysterectomy, salpingectomy or oophorectomy)²⁹.

The subject will also be instructed to contact the Investigator immediately if, at any time during the study, subject thinks she might be pregnant.

If a subject experiences a micro-insert expulsion or removal during or following the NovaSure procedure, subject will be followed for the duration of the adverse event, then terminated from the study.

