7.4.1.3 Assessments and documentation of adverse events³⁸ - amended

Investigators must collect all AEs for each subject from the time of signing of the informed consent through the end of subject study participation, whether or not deemed related to the investigational device or procedure. All AE data will be recorded on the CRFs as well as documented in the subject's medical record and study source documents.³⁹

All SAEs and SADEs will be followed until the event has subsided or, in case of permanent impairment, until the event stabilizes and the overall clinical outcome has been ascertained.

Investigator must determine whether adverse event meets the definition of a serious adverse event; if so, it must be reported as required by Section 7.4.1.1.

Any SAE or incident will be reviewed and processed by the sponsor according to all applicable regulations.

Investigators must document all device failures, malfunctions and use errors, including the assessment of whether the event is considered an incident (ADE) using the Device Malfunction and Failure CRF.

Because an approved device will be used for the placement procedure, any device malfunctions will be reported to the sponsor's Product Surveillance department. Device malfunctions will not be analyzed as part of this study as the placement procedure and devices are not being evaluated.

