13.4.1.3 Modification 3: modification of the Bayer template language regarding withdrawal criteria

Rationale for change: Since compliance with wearing the device is not an issue as it is permanent, this language is being removed.

Sections affected by this modification:

- [Section 5.2.1 Withdrawal](#)

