6.2.2 Secondary Endpoint Analyses

The secondary endpoint in the PAS is the incidence of adverse events when NovaSure EA is performed in the presence of Essure micro-inserts. There is no specific study hypothesis. Instead, the safety profile will be analyzed using summary statistics on the Safety Cohort as described in Section 6.3.

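### Protocol 5.2.1 lets the investigator end a treated woman's follow-up for an adverse event or an unlisted reason, although only telephone calls remain after week 1, so later events can go unrecorded

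*Protocol*

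**What the plan says.** **Termination rule.** Current Protocol 5.2.1, whose wording the Amendment 6 log repeats, permits termination by the investigator and introduces the grounds with "Reasons for termination of a subject from the study may include, but are not limited to, the following". Among those listed are "An adverse event (AE) preventing study participation" and "Subject does not retain device (e.g. due to removal of device, expulsion, salpingectomy or other utero-tubal surgeries". A separate clause in 5.2.1 makes withdrawal mandatory when the investigator judges that continuing would harm the woman.

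**What Amendment 6 changed.** It deleted withdrawal at the sponsor's request, with the rationale "Since compliance with wearing the device is not an issue as it is permanent, this language is being removed" (Protocol 13.4.1.3). The investigator's discretion was left as it stood.

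**What remains after week 1.** NovaSure is a single Day 0 procedure. After the one-week office visit, the physician's office contacts the woman at years 1, 2 and 3 "to have a telephone follow-up visit" (Protocol 7.1.2.4). Those calls ask about pregnancy, AEs and extirpative surgery.

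**What is collected, and for how long.** AEs are collected "from the time of signing of the informed consent through the end of subject study participation" (Protocol 7.4.1.3). The duty to report a pregnancy is likewise tied to the woman's participation (Protocol 7.4.3). For the primary endpoint she contributes woman-months only while she participates (Protocol 8.4.1).

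**What the data are for.** SAP 6.2.2 states: "The secondary endpoint in the PAS is the incidence of adverse events". There is no safety hypothesis.

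**The concern.** No study treatment is left to stop after Day 0, so terminating a treated woman ends only observation. The documents do not explain how an AE would prevent a yearly telephone call, and they do not say that calls continue after termination.

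Where the reason for termination is an AE, censoring is tied to the secondary endpoint and may be informative: a woman who has had one problem may be more likely to have another. She remains in the safety cohort and can add no later events. The SAP's AE tables count events and subjects without adjusting for exposure (SAP 6.3.1), missing data are not imputed apart from AE dates (SAP 4.3), and no sensitivity analysis for AE-related termination is planned. The Kaplan-Meier analysis is supportive, covers pregnancy only, and itself assumes non-informative censoring.

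Two things are at stake: the incidence of later AEs, which could be understated, and the pregnancy analysis, which could lose woman-months or miss a pregnancy.

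**Working it through.** **Inputs.** Enrolment is at least 220 and follow-up is 36 months (Protocol 4). The prior is beta(0.5, 0.5) on the monthly rate (Protocol 8.4.1). The 3-year threshold is 2.8%, judged at 97.5% posterior probability (SAP 6.2.1). The documents give no termination rate, so 2%, 5% and 10%, each at 1 year on average, are assumptions.

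**Formula.** With f pregnancies in w woman-months, the upper limit over k months is 1 − (1 − q)^k, where q is the 97.5% quantile of beta(0.5 + f, 0.5 + w − f).

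**1. The plan's own figures.** For w = 2,400 and k = 12:
- f = 0: q = 0.00105, limit 1.25% (stated 1.25%).
- f = 1: q = 0.00195, limit 2.31% (stated 0.023).

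Both are reproduced.

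**2. Lost exposure, 3-year limit with one pregnancy.** Full follow-up is 220 × 36 = 7,920 woman-months. A woman terminated at 1 year loses 24.

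| Terminated (assumed) | Women | Woman-months lost | Left | Upper limit, f = 1 |
|---|---|---|---|---|
| 0% | 0 | 0 | 7,920 | 2.10% |
| 2% | 4.4 | 106 | 7,814 | 2.13% |
| 5% | 11 | 264 | 7,656 | 2.17% |
| 10% | 22 | 528 | 7,392 | 2.25% |

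All are below 2.8%.

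**3. Losses needed to cross 2.8%.** With one pregnancy the limit stays under 2.8% down to about 5,926 woman-months. That is a loss of 7,920 − 5,926 = 1,994, and 1,994 / 24 is about 83 women, or 38% of 220. With no pregnancy, about 3,184 woman-months are enough. With two, the limit is 2.88% even at 7,920, so the criterion fails whatever the terminations.

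**4. A missed pregnancy.** At 7,392 woman-months:
- One recorded pregnancy gives 2.25%, a pass.
- A second gives 3.08%, a fail. Had the calls continued and all 7,920 woman-months been observed, two would give 2.88%, also a fail.

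Missing the second pregnancy would therefore turn a fail into a pass. At 1 year and 2,400 woman-months, the same applies to a single pregnancy: 1.25% without it and 2.31% with it, against 2.1%. These reversals rest on the SAP's 97.5% level. At the 95% level that Protocol 8.6 sets for the 1-year rate, one pregnancy gives 1.94% and passes; applying 95% to the 3-year rate, two at 7,392 give 2.66% and pass.

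**5. Later AEs (illustration only).** Let a share d of women be terminated before any later AE, with RR times the later-AE risk of those who stay. The share of later-AE cases missed is d·RR / (1 − d + d·RR):
- d = 5%, RR = 1: 0.05 / 1.00 = 5%
- d = 10%, RR = 2: 0.20 / 1.10 = 18%
- d = 20%, RR = 2: 0.40 / 1.20 = 33%
- d = 20%, RR = 4: 0.80 / 1.60 = 50%

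Neither d nor RR is in the documents. The AE that led to termination is counted in every case.

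**The case against.** The plan has real safeguards. The safety cohort is defined by an attempted procedure, and dropouts stay in every analysis set they qualify for (Protocol 8.2; SAP 4.2 and 5). Serious events are followed until they subside or stabilize, and those arising after the observation period are still processed by the sponsor (Protocol 7.4.1.3 and 7.4.1.4). Reasons for withdrawal must be recorded, and all reasons for early termination are summarized (Protocol 5.2.1; SAP 6.1). The listed AE ground is limited to an AE that prevents participation, which should seldom apply to a telephone call. Amendment 6 narrowed the withdrawal rules, and safety is a secondary, descriptive endpoint.

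Most of this stands, and it rules out two stronger readings that a reader might infer:

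- *That women with complications can be selectively dropped from the safety study.* They stay in the cohort with their triggering AE counted; only later follow-up is lost. Nothing in the documents shows selective use, and a discretionary termination need not follow an event at all.
- *That avoidable terminations alone could turn a 3-year pass into a fail.* None of the assumed rates does so. With one pregnancy it would take about 38% of women terminated at 1 year, or large attrition from other causes.

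The safeguards do not close the remaining gap. Following a known serious event does not reveal a new non-serious one. Processing a later serious event presupposes that someone hears of it, and no contact is scheduled after termination. Tabulating reasons shows the loss without recovering the data.

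**Conclusion.** The concern holds as a gap in follow-up wording. Protocol 5.2.1 allows observation of a treated woman to end for an AE or an unlisted reason when only telephone contact is left. New AEs, surgery and pregnancies after that point can go unrecorded while she remains in the denominator, so later-AE incidence can be biased downward.

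The size is unknown because no termination rate is documented. The effect of lost exposure is small: 2.10% to 2.25% in the largest scenario assumed. An unrecorded pregnancy matters more and could change the decision under the SAP's 97.5% rule, but nothing shows that this is likely. This is a cheap improvement, not a threat to the study's validity.

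**What to change.** In Protocol 5.2.1:

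- State that, after NovaSure, an AE or a discretionary decision does not by itself end the scheduled 1-, 2- and 3-year calls. They continue unless the woman withdraws consent, dies, cannot be contacted, or must be withdrawn under the existing well-being clause. That clause has to be kept, because a blanket statement that no investigator decision ends follow-up would contradict it.
- Remove the open-ended wording of the termination list for treated women.
- Reconcile the insert-loss text. Section 5.2.1 makes termination optional when the device is not retained, whereas 7.1.2.5 says of expulsion or removal that the "subject will be followed for the duration of the adverse event, then terminated from the study".

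As a complement, the SAP could report AEs and exposure time by reason for termination and add one sensitivity analysis for AE-related termination.

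Cost: a few extra calls of a kind already in the schedule, and an amendment that each principal investigator must sign before it takes effect at the center (Protocol 3).

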13.4.2.6 Section 6.3 Treatment assignment

Section revised per modification 1.

Old text:

[...]

A subject may not be enrolled in the study until she has ~~an~~ Essure confirmation test done that documents bilateral satisfactory device location and fallopian tube occlusion. If subject has had Essure placement but she does not have an Essure Confirmation Test that documents bilateral satisfactory device location and fallopian tube occlusion, she may repeat the Essure Confirmation Test.

New text:

[...]

A subject may not be enrolled in the study until she has a successful Essure confirmation test done that documents bilateral satisfactory device location and fallopian tube occlusion noted on HSG OR optimal or satisfactory micro-insert location noted on TVU. If subject has had Essure placement but she does not have an Essure Confirmation Test that documents bilateral satisfactory device location and fallopian tube occlusion on HSG OR optimal or satisfactory micro-insert location on TVU, she may repeat the Essure Confirmation Test.

13.4.2.7 Section 7.1.2.1 Eligibility and Screening Visit (-30 days)

Section revised per modification 1.

Old text:

[...]

- Inform the subject of the Essure-NovaSure PAS. Subject will not enroll in the study until she has ~~an~~ Essure confirmation test that documents bilateral satisfactory device location and fallopian tube occlusion. If subject has had Essure placement but she does not have an Essure Confirmation Test that documents bilateral satisfactory device location and fallopian tube occlusion, she may repeat the Essure Confirmation Test.

[...]

New text:

[...]

- Inform the subject of the Essure-NovaSure PAS. Subject will not enroll in the study until she has a successful Essure confirmation test that documents bilateral satisfactory device location and fallopian tube occlusion noted on HSG OR optimal or satisfactory micro-insert location noted on TVU. If subject has had Essure placement but she does not have an Essure Confirmation Test that documents bilateral satisfactory device location and fallopian tube occlusion on HSG OR optimal or satisfactory micro-insert location on TVU, she may repeat the Essure Confirmation Test.

[...]

13.4.2.8 Section 7.1.2.4 One-, Two- and Three-Year Post-EA Phone Call (\pm 28 days)

Section revised per modification 4.

Old text:

[...]

The 3-year phone call will be the final visit in the study. If the subject reports an adverse event or pregnancy during the 3-year follow-up phone call, the subject will be followed until event resolution. If a pregnancy or adverse event was previously reported but event is not resolved during the 3-year phone call, event will be followed until resolution. ~~If no adverse events or pregnancies are reported, the Study Completion or Early Termination CRF will be completed after the 3-year phone call.~~

New text:

[...]

The 3-year phone call will be the final visit in the study. If the subject reports a serious adverse event or pregnancy during the 3-year follow-up phone call, the subject will be followed by the sponsor's pharmacovigilance department until event resolution or stabilization. If a pregnancy or serious adverse event was previously reported but the event is not resolved during the 3-year phone call, the event will be followed by the sponsor's pharmacovigilance department until resolution. Information pertaining to these events will be collected and archived in the sponsor's pharmacovigilance database.

